8.4. Sample Size Determination

Due to the exploratory nature of the study, the sample size is not based on formal statistical considerations. The sample size is based on experience from similar studies to obtain adequate preliminary efficacy, safety, and tolerability data to achieve the objectives of the study.

8.5. Analysis Populations

Statistical analysis will be conducted on all enrolled subjects.

8.6. Statistical Analyses

This section presents a summary of the planned statistical analyses. A Statistical Analysis Plan (SAP) that describes the details of the analyses to be conducted will be finalized prior to database lock.

Summary statistics will be provided for the variables described as follows. For continuous variables, these statistics will typically include the number of subjects, mean, standard deviation, median, minimum, and maximum. For categorical variables, these statistics will typically include the number and percentage of subjects in each category.

8.6.1. Study Subjects and Demographics

8.6.1.1. Disposition and Withdrawals

The numbers of subjects assigned, completing, and withdrawing, along with reasons for withdrawal, will be tabulated overall and by treatment group. The number of subjects in each analysis population will be reported.

8.6.1.2. Protocol Deviations

Protocol deviations will be identified and classified as minor or major.

8.6.1.3. Demographics and Other Baseline Characteristics

These analyses will be conducted for the safety populations.

Demographic and baseline characteristics (including age, gender, race, weight, height, and BMI) will be summarized by treatment group and for the overall population by descriptive statistics. No formal statistical analyses will be performed. Medical history, clinical laboratory test results, and ECG assessments will be listed and summarized by descriptive statistics.

Prior and concomitant medications will be summarized by treatment group and by the number and percentage of subjects taking each medication. They will also be classified by using the World Health Organization Drug Dictionary Anatomical Therapeutic Chemical classes and preferred terms.

8.6.2. Exposure and Compliance

The exposure to study medication will be summarized by descriptive statistics. Any compliance deviations will be listed.

8.6.3. Efficacy Analyses

The results of the video-EEG (including presence or absence of hyperventilation), CGI-I, and seizure diary assessments will be summarized using summary tables, listings, and figures (TLFs), as appropriate. Continuous variables will be summarized using descriptive statistics: sample size (n), mean, standard deviation (SD), or coefficient of variation (CV %) as appropriate, median, interquartile range, minimum and maximum. Categorical variables will be summarized by presenting the number (frequency) and percentage in each category.

8.6.4. Safety and Tolerability Analyses

Safety analyses will be conducted using data from the safety population. No formal inferential analyses will be conducted for safety variables. Data listings will be provided for protocol-specified safety data.

8.6.4.1. Adverse Events

The Medical Dictionary for Regulatory Activities (MedDRA, version 20.0 or higher) will be used to classify all AEs. Adverse event summaries will include only TEAEs, which will be summarized for each treatment group.

The number and percentage of subjects with AEs will be displayed for each treatment group by system organ class and preferred term. Summaries of AEs by severity and relationship to the IP will also be provided. Serious AEs (SAEs) and AEs resulting in discontinuation will be summarized separately in a similar manner. Patient listings of AEs and SAEs will be produced.

8.6.4.2. Clinical Laboratory Evaluations

For the continuous hematology and chemistry laboratory parameters, descriptive statistics will be presented for values collected at Screening (Visit 1), Treatment Period (Visits 3, 4, and 6 [End of Study]) or the Early Withdrawal Visit, and for any clinically significant changes from Screening. For urinalysis, descriptive statistics will be presented for values collected at Screening (Visit 1), and at Visit 6 (End of Study) or the Early Withdrawal Visit, and for any clinically significant changes from Screening

8.6.4.3. Vital Signs

For blood pressure, pulse rate, temperature, and respiration rate, descriptive statistics will be presented for values collected at Screening (Visit 1), Baseline (Visit 2), Treatment Period (Visits 3, 4, and 6 [End of Study]) or the Early Withdrawal Visit, and for the changes from Baseline to Visit 6 (End of Study) / Early Withdrawal.

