The results of the video-EEG (including presence or absence of hyperventilation), CGI-I, and seizure diary assessments will be summarized using summary tables, listings, and figures (TLFs), as appropriate. Continuous variables will be summarized using descriptive statistics: sample size (n), mean, standard deviation (SD), or coefficient of variation (CV %) as appropriate, median, interquartile range, minimum and maximum. Categorical variables will be summarized by presenting the number (frequency) and percentage in each category.

Safety Analysis

All safety assessments, including AEs, clinical laboratory evaluations, vital signs, 12-lead ECGs, C-SSRS (children and adolescents aged 7 to 17 years, if appropriate), concomitant AED blood levels, physical and neurological examinations will be listed. When appropriate, they will be summarized with descriptive statistics by age and dose cohort. The Medical Dictionary for Regulatory Activities (MedDRA; Version 20.0 or higher) will be used to classify all adverse events with respect to system organ class and preferred term. Adverse event summaries will include only TEAEs, which will be summarized for each treatment group.

Clinical laboratory findings and vital signs will be summarized for all patients for observed values and change from baseline. Shifts from baseline according to normal range criteria will also be presented for all patients.

The neurological examination results will be listed and summarized descriptively. Shifts from baseline according to normal and abnormal criteria will also be presented for all patients in the safety population.

Results of physical examinations conducted throughout the study will be presented in listings and summarized descriptively. Shifts from baseline according to normal and abnormal criteria will also be presented for all patients in the safety population.

Prior medication and concomitant medications will be reported in the data listings.

Statistical analyses will be performed using SAS® (Version 9.3 or higher, SAS Institute Inc.) or R (Version 3.3 or higher, Roswell Park Cancer Institute).

Pharmacokinetic Analysis

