- There were no clear trends for age-related differences in cannabidiol exposures, but exposure in infants tended to be lower than that in children and adolescents, approximately half at the highest dose (40 mg/kg/day).
- Approximately 50% of subjects enrolled were receiving clobazam. Clobazam and cannabidiol have a reciprocal drug-drug interaction leading to the increased mean exposures of both cannabidiol (approximately 2.5-fold), and clobazam as well as norclobazam (approximately 3-fold) at the highest dose (40 mg/kg/day).
- No apparent gender differences were observed for cannabidiol pharmacokinetics (PK).
- Pharmacokinetic results for 7-hydroxy cannabidiol and its statistical evaluations generally reflected those observed for parent cannabidiol.
- There were no quantifiable levels Δ^9 -THC and 11-hydroxy- Δ^9 -THC measured following cannabidiol dosing.
- All doses of the investigational product were generally well-tolerated, although dose-titration was not employed. Dose-dependent adverse events (AEs) that occurred in multiple dosing cohorts and increased as the dose of the investigational product increased included diarrhea, flatulence, weight increase, somnolence, and psychomotor hyperactivity. Events of somnolence were potentially also related to concomitant use of clobazam with the investigational product, but this was not formally investigated in this study.
- There were no clinically relevant differences in the AE profile among subjects in the infant, child, and adolescent age categories.
- Serious adverse events were reported rarely and were consistent with underlying disease or procedures.
- Although this was not designed as an efficacy study, parent(s)/caregiver(s) and investigators both reported notable reductions in severity of mental illness (Clinical Global Impression of Severity) and improvement in global subject status (Clinical Global Impression of Improvement).

- The average change in weekly seizure rates (seizures of all types) was variable across subjects, dosing cohorts, and over time. Although the mean change in the weekly rate tonic seizures at the end of the study compared with baseline generally decreased in a potentially dose-dependent manner, no pattern was observed for the other types of seizures reported. It was thought that tonic seizures were most representative of seizure control in this study.

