6.2.2. Physical Examinations

A physical examination will be conducted for every patient during the Screening Visit (Visit 1). The examination will include evaluation of general appearance, skin, eyes, ears, nose, throat, neck, lymph nodes, chest, heart, abdomen, and extremities. Height and weight will be measured during Visits 1, 3, 6 (End of Study) or the Early Withdrawal Visit.

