8.2. Safety Endpoints

Changes in safety endpoints will be reported as mean/median change from baseline at relevant time points and as a listing of events that fall outside normal limits.

- Incidence, type, and severity of AEs and serious adverse events (SAEs) occurring during the Treatment Period (i.e., treatment-emergent AEs [TEAEs]).
- Changes from Baseline (Visit 2) in vital signs during the Treatment Period.
- Changes from Screening in laboratory values (hematology, chemistry, and urinalysis) during the Treatment Period.

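### Sections 8.6.4.2 and 8.6.4.3 summarise laboratory and vital-sign change more narrowly than Section 8.2 and the synopsis promise, and the laboratory rule selects on the outcome it describes

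*Protocol*

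**What the plan says.** **The commitment.** Protocol Section 8.2 sets a general rule: "Changes in safety endpoints will be reported as mean/median change from baseline at relevant time points", plus a listing of out-of-range events. It then names two measured endpoints: "Changes from Screening in laboratory values (hematology, chemistry, and urinalysis) during the Treatment Period" and "Changes from Baseline (Visit 2) in vital signs during the Treatment Period". Neither is restricted to notable changes or to the last visit. The synopsis (Safety Analysis) agrees: "Clinical laboratory findings and vital signs will be summarized for all patients for observed values and change from baseline". It adds shift tables against the normal range for all patients.

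**The analysis sections.** Section 8.6.4.2 summarises hematology and chemistry values at Screening and at Visits 3, 4 and 6 or Early Withdrawal, and urinalysis at Screening and at Visit 6 or Early Withdrawal. For change, it offers descriptive statistics only "and for any clinically significant changes from Screening". Section 8.6.4.3 summarises vital-sign values at every scheduled measurement, but change statistics only "for the changes from Baseline to Visit 6 (End of Study) / Early Withdrawal".

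**Weight.** Section 6.2.2 states: "Height and weight will be measured during Visits 1, 3, 6 (End of Study) or the Early Withdrawal Visit". Weight is not among the vital signs defined in Section 6.2.4 and is not a Section 8.2 endpoint. Its only stated summary is as a baseline characteristic (Section 8.6.1.3).

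**The concern.** Whoever programs the tables has two instructions for the same endpoint, and the more specific one is the weaker. A mean or median taken only over laboratory changes judged clinically significant describes the children picked out by that judgement, not the cohort. The study is open-label and Section 8.6.4.2 states no criterion, so the judgement may vary between investigators and cohorts.

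For vital signs, the omitted change at Visit 4 is the only scheduled vital-sign assessment between the start of the Treatment Period and its end.

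At stake is how well the three doses can be described for within-child change. Section 6.2.8.1 names transaminase elevation as an adverse event of special interest, so the laboratory limb is the more important one.

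**Working it through.** The protocol gives no figure on this point, and Section 8.4 gives no formal sample-size basis, so there is nothing to reproduce. The check compares the texts and then asks what the stated tables can and cannot supply.

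**1. Texts side by side**

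| Item | Section 8.2 and synopsis | Section 8.6.4 |
|---|---|---|
| Laboratory change | From Screening, during treatment, unfiltered | Clinically significant changes only |
| Vital-sign change | From Visit 2, during treatment | Visit 6/Early Withdrawal only: 1 of the 3 scheduled post-baseline visits (3, 4, 6) |
| ECG change (Section 8.6.4.4) | Not named as an endpoint | Screening to Visit 6/Early Withdrawal, unfiltered |

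The ECG row shows that the document uses the unfiltered form elsewhere. Laboratory change is the exception.

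**2. What the filter does (illustration; all values assumed)**

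Suppose individual change, in units of its own SD, is normal with mean *s*, and a change counts as clinically significant above a cut *c* of 2 to 3 SD. Section 8.6.4.2 gives no cut, so the range is an assumption. With 10 children per cohort (Section 4.4):

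- Chance that one child is flagged: p = 1 − Φ(c − s).
- Chance that none of 10 is flagged: (1 − p)^10.
- Mean of the flagged changes: s + φ(c − s)/p.

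| Shift s | p (c = 2; c = 3) | None of 10 flagged (c = 2; c = 3) | Mean of flagged changes (c = 2) |
|---|---|---|---|
| 0 | 0.0228; 0.0013 | 79%; 99% | 2.37 |
| 0.3 | 0.0446; 0.0035 | 63%; 97% | 2.41 |
| 0.5 | 0.0668; 0.0062 | 50%; 94% | 2.44 |
| 1.0 | 0.1587; 0.0228 | 18%; 79% | 2.53 |

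For s = 0.5 and c = 2: p = 1 − Φ(1.5) = 0.0668; (1 − 0.0668)^10 = 0.50; 0.5 + 0.1295/0.0668 = 2.44.

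The filtered summary is often empty. When it is not, its mean hardly moves: from 2.37 to 2.53 SD while the true shift goes from 0 to 1 SD. The unfiltered mean change in 10 children estimates the shift itself, with a 95% half-width of 2.262/√10 = 0.72 SD.

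**3. What the visit tables still give**

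- *Mean, complete data.* The mean change equals the difference of visit means. A simulated paired sample of 10 gave 2.400 both ways.
- *Median.* In the same sample the median change was 2.16 and the difference of medians was 2.31. Section 8.2 names the median, and visit summaries do not supply it.
- *Spread.* The SD of change was 1.89. It depends on the within-child correlation, which visit summaries do not report.
- *Mean, after dropout.* Suppose *d* of 10 children have no value at a later visit. Let C be the Screening mean of those remaining and D that of those missing. The difference of visit means equals the mean change plus C − (C(10 − d) + dD)/10 = (d/10)(C − D). With one or two children missing, the error is one tenth or one fifth of the gap between the groups.

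Section 8.6.7 rules out imputation, and Section 3.5 discontinues children on transaminase criteria, so missing values may be related to the variable being summarised. An Early Withdrawal value can fill the last row, but not a missed Visit 4.

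**4. Which visits are comparable across cohorts**

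Section 7.2.1 dispenses drug at Visit 2 only to Cohort 2. Section 7.3.1 trains Cohorts 1 and 3 to dose at Visit 3. A Visit 3 change therefore follows 5 days of drug in Cohort 2 and comes before or at the first dose in Cohorts 1 and 3. Visit 4 is the only omitted vital-sign change at which all three cohorts are clearly on treatment.

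**The case against.** **Section 8.6 calls itself a summary and leaves detail to the analysis plan.** That is fair for detail, and that plan is not at hand. But the conflict is in the protocol's own text: an analysis plan could follow either wording and claim to comply.

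**Section 8.2 says relevant time points, and the last visit is one.** This carries some weight and makes the vital-sign limb the weaker of the two. Against it, the endpoint line covers the Treatment Period and the synopsis does not single out the last visit.

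**A reader might infer that dose-related shifts below a clinical threshold are lost, so the doses could look equally safe.** The documents do not support this. Values are summarised at every scheduled visit, and the synopsis adds normal-range shift tables. Section 8.6.4.2 states no numeric threshold, and Section 6.2.8.1 allows a within-range shift to be an adverse event when judged clinically important. The illustration above concerns the filtered summary alone, not everything the plan reports.

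**A reader might also count weight change as an undelivered endpoint**, since Section 1.3 lists among dose-dependent events "diarrhea, flatulence, weight increase, somnolence, and psychomotor hyperactivity". But Section 8.2 promises no weight endpoint, the Section 1.3 finding concerns adverse events, and weight gain reported as a treatment-emergent event is tabulated under Section 8.6.4.1.

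**Conclusion.** The point holds as an internal contradiction plus one poorly chosen rule. Section 8.6.4.2 conflicts with Section 8.2 and the synopsis and conditions its change summary on the outcome. Section 8.6.4.3 is narrower than Section 8.2 and gives no change at Visit 4.

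Severity is minor to moderate, and no figure in the plan changes. What would be missing if Section 8.6.4 were followed literally is the median and SD of within-child change for laboratory values at all visits and for vital signs before Visit 6, and an exact mean change where children have dropped out. The textual conflict needs no assumption. The figures for the filtered summary rest on an assumed normal model and assumed cuts of 2 to 3 SD, and only show direction.

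**What to change.** - **Section 8.6.4.2:** replace the clause on clinically significant changes with change from Screening for all patients, by cohort, at each scheduled post-Screening visit (Visits 3, 4 and 6/Early Withdrawal for hematology and chemistry; Visit 6/Early Withdrawal for urinalysis). List clinically significant changes in addition.
- **Section 8.6.4.3:** add change from Baseline (Visit 2) at Visit 4.
- **Any Visit 3 change:** label it as after 5 days of drug in Cohort 2 and before or at first dose in Cohorts 1 and 3, so that it is not read as a dose comparison.
- **Optional:** a table of weight change by cohort. It should start from Visit 1, the only pre-drug weight common to all cohorts; by Visit 3 Cohort 2 has already been dosed.

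The cost is wording and slightly longer safety tables. No new data are needed.

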8.6.4.4. Electrocardiograms

For the continuous ECG parameters, descriptive statistics will be presented for values collected at Screening (Visit 1), Visit 6 (End of Study) or the Early Withdrawal Visit, and for the changes from Screening (Visit 1) to Visit 6 (End of Study)/Early Withdrawal.

Additionally, the number and percentage of subjects will be presented as shift tables for the overall interpretation from Screening (normal or abnormal, not clinically significant [NCS]) to End of Study/Early Withdrawal (normal; abnormal, NCS; or abnormal, clinically significant [CS]).

8.6.4.5. Physical Examination Findings

Physical examination body systems will be presented as the number and percentage of subjects that have normal or abnormal results at Screening (Visit 1). The examination will include evaluation of general appearance, skin, eyes, ears, nose, throat, neck, lymph nodes, chest, heart, abdomen, and extremities.

8.6.4.6. Columbia Suicide Severity Rating Scale (C-SSRS)

C-SSRS categorization based on Columbia Classification Algorithm of Suicide Assessment (C-CASA) categories 1, 2, 3, 4, and 7 will be summarized as dichotomous endpoints at Screening (Visit 1), Treatment Period (Visit 5) or the Early Withdrawal Visit.

8.6.5. Interim Analysis

No interim analyses are planned.

8.6.6. Pharmacokinetic Analyses

Descriptive statistics of trough plasma concentration and PK parameters data for CBD and 7-OH CBD by Visit, Dose, and Response will be provided. The following noncompartmental PK parameters will be estimated from the plasma concentration-time data: area under the curve from time 0 to the last measured concentration (AUC_{0-t}) by maximum plasma concentration (C_{max}), and time to reach maximum plasma concentration (T_{max}) using Phoenix WinNonlin (Version 6.3 or higher; Pharsight Corporation, Cary, NC 27518, USA). Additional PK parameters may be estimated, as appropriate. Exploratory analysis of dose (exposure)-response relationship will be performed. Further population PK approach may be used for PK parameter estimation, as appropriate.

8.6.7. Missing Data

There will be no imputation of the missing values for the efficacy, safety, or PK population. All assessments will be conducted based on all the observed data.

9. STUDY CONDUCT

Steps to ensure the accuracy and reliability of data include the selection of qualified investigators and appropriate study sites, review of protocol procedures with the investigator and associated personnel prior to the study, periodic monitoring visits, and meticulous data management.

9.1. Sponsor and Investigator Responsibilities

9.1.1. Sponsor Responsibilities

The sponsor, and/or sponsor's representative is obligated to conduct the study in accordance with strict ethical principles. The sponsor reserves the right to withdraw a patient from the study, to terminate participation of a study site at any time, and/or to discontinue the study.

The sponsor, or sponsor's representative, agrees to provide the investigator with sufficient material and support to permit the investigator to conduct the study according to the study protocol.

9.1.2. Investigator Responsibilities

By signing the Investigator's Agreement, the investigator indicates that she/he has carefully read the protocol, fully understands the requirements, and agrees to conduct the study in accordance with the procedures and requirements described in this protocol.

The investigator also agrees to conduct this study in accordance with all laws, regulations, and guidelines of the pertinent regulatory authorities, including and in accordance with the April 1996 International Conference on Harmonisation (ICH) Guidance for Industry E6 Good Clinical Practice (GCP) and in agreement with the 1996 Version of the Declaration of Helsinki. While delegation of certain aspects of the study to sub-investigators and study coordinators is appropriate, the investigator will remain personally accountable for closely overseeing the study and for ensuring compliance with the protocol and all applicable regulations and guidelines. The investigator is responsible for maintaining a list of all persons that have been delegated study-related responsibilities (e.g., sub-investigators and study coordinators) and their specific study-related duties.

Investigators should ensure that all persons who have been delegated study-related responsibilities are adequately qualified and informed about the protocol, IPs, and their specific duties within the context of the study. Investigators are responsible for providing CRO with documentation of the qualifications, GCP training, and research experience for themselves and their staff as required by the sponsor and the relevant governing authorities.

To ensure compliance with the guidelines, the study will be audited by an independent person. The investigator agrees, by written consent to this protocol, to cooperate fully with compliance checks by allowing access to all study documentation by authorized individuals.

